Study Protocol

Title of the study: Split-in-situ Resection With Radio-frequency Ablation Instead of Liver Partition on the First Stage (RALPPS) in Patients With Hilar and Intrahepatic Cholangiocarcinoma

Unic Protocol ID: MCNC 09/2017

Date: October 24, 2017

Background: Unsatisfactory immediate outcomes of Associating liver partition and portal vein ligation for staged hepatectomy (ALPPS) in surgery of cholangiocarcinoma suggested that patients with biliary cancer should not be treated by ALPPS. Short-term results of ALPPS variants with reduced surgical trauma on the first stage in patients with cholangiocarcinoma were not yet estimated.

Study design: retrospective observational case-control study.

The purpose of the study: comparison of short-term results of RALPPS and portal vein embolization (PVE) in patients with hilar (h-CCA) and intrahepatic (i-CCA) cholangiocarcinoma.

Material and Methods: two groups will be compared.

Group 1: patients with h-CCA and i-CCA underwent RALPPS.

Group 2: patients with h-CCA and i-CCA underwent PVE.

Inclusion Criteria: patients with h-CCA and i-CCA which are the candidates for radical treatment (intention to R0 resection) using major liver resection with volume of future liver remnant (FLR) less than 40%.

Indication for RALPPS/PVE.

- h-CCA, type II-IV, T1-3N0-1M0, volume of FLR<40%
- i-CCA, T1-3N0-1M0, volume of FLR<40%

Contraindication for RALPPS/PVE.

- h-CCA, stage IVA, B
- i-CCA, stage IVB
- i-CCA, T4N0-1M0
- i-CCA, h-CCA with volume of FLR >45%
- acute cholangitis and/or infected fluid collections, liver abscesses, other unresolved surgical complications of biliary draining procedures.
- jaundice with total bilirubin >50 μ mol/L
- prior anamnestic allergic reaction or any other sign of intolerance to iodinated contrast media

Inclusion Criteria

- Gender: both, male and female
- Minimum age 18 years
- Maximum age: 80 years

Exclusion Criteria

- Age under 18 years
- Age above 80 years
- Persons who are incapable of giving consent
- Pregnant or breast-feeding women

Preoperative examination:

1. Abdominal ultrasound examination,
2. Abdominal enhanced CT (with or without MRI and MRCP),
3. Direct cholangiography,
4. Chest CT,
5. The upper digestive tract endoscopic examination,
6. Colonoscopy (if it is absent over the past year),
7. Tumor markers (CEA and CA 19-9).

Comparative analysis should include following intraoperative and postoperative factors

Primary endpoint: rate of FLR hypertrophy (%).

The standard formula for calculation the rate of hypertrophy:

$$[(\text{Post-PVE FLR} - \text{Pre-PVE FLR}) / (\text{Pre-PVE FLR})] \times 100$$

Secondary endpoints:

1. Morbidity after stage 1 (according to Clavien-Dindo classification, [attachment 1](#))
2. Morbidity after stage 2
3. Blood loss (during stage 2)
4. Duration of hospital stay

Bile leakage will be classified in severity according to the international study group for liver surgery ([attachment 2](#)).

Posthepatectomy liver failure was estimated according to the international study group for liver surgery ([attachment 3](#)).

The number of patients for primary estimation of short-term results consist of 10 patients in RALPPS group and 20 patients in group of PVE. If preliminary results reveal tendency to better results of RALPPS in terms of FLR hypertrophy and confirm safety of RALPPS the number of patients will be increased to 60 (30 patients in each group).

[name], PhD,
Head of the HepatoPancreatoBiliary
Surgery Department,
Moscow Clinical Scientific Center
[contact]
www.mknc.ru

Attachments 1

CLAVIEN-DINDO GRADING SYSTEM FOR THE CLASSIFICATION OF SURGICAL COMPLICATIONS

Grades	Definition
Grade I:	Any deviation from the normal postoperative course without the need for pharmacological treatment or surgical, endoscopic and radiological interventions. Allowed therapeutic regimens are: drugs as antiemetics, antipyretics, analgetics, diuretics and electrolytes and physiotherapy. This grade also includes wound infections opened at the bedside.
Grade II:	Requiring pharmacological treatment with drugs other than such allowed for grade I complications. Blood transfusions and total parenteral nutrition are also included.
Grade III:	Requiring surgical, endoscopic or radiological intervention
Grade III-a:	Intervention not under general anesthesia
Grade III-b:	Intervention under general anesthesia
Grade IV:	Life-threatening complication (including CNS complications: brain haemorrhage, ischaemic stroke, subarachnoid bleeding, but excluding transient ischaemic attacks) requiring IC/ICU management.
Grade IV-a:	Single organ dysfunction (including dialysis)
Grade IV-b:	Multi-organ dysfunction
Grade V:	Death of a patient
Suffix 'd':	If the patient suffers from a complication at the time of discharge, the suffix "d" (for 'disability') is added to the respective grade of complication. This label indicates the need for a follow-up to fully evaluate the complication.


Attachments 2

Bile leakage

Bile leakage grade A: Grade A bile leakage has little or no impact on patients' clinical management.

Bile leakage grade B: A bile leakage requiring a change in patients' clinical management but can be treated without relaparotomy.

Bile leakage grade C: Patients with a Grade C bile leakage require relaparotomy to control this complication.

Attachments 3

Posthepatectomy liver failure

Grade A posthepatectomy liver failure: Grade A PHLF represents a postoperative deterioration of liver function that does not require a change in the patient's clinical management.

Grade B posthepatectomy liver failure: Patients are diagnosed with grade B PHLF if there is a deviation from the regular, postoperative clinical pathway, but they can be managed without invasive treatment.

Grade C posthepatectomy liver failure: Patients who develop PHLF requiring an invasive procedure are classified as having grade C PHLF.

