Statistical analysis plan

Title of the study: Split-in-situ Resection With Radio-frequency Ablation Instead of Liver Partition on the First Stage (RALPPS) in Patients With Hilar and Intrahepatic Cholangiocarcinoma

Unic Protocol ID: MCNC 09/2017

Date: October 24, 2017

Statistical analysis

The propensity score matching (PSM) method was used to overcome heterogeneity of retrospectively collected data in compared groups. Nearestneighbor algorithm with 1:1 match ratio using a 0.2 caliper was applied. Matching for stage 1 included following factors: maximum total bilirubin level, duration of jaundice and acute cholangitis presence. PSM model for stage 2 enrolled FLR volume after portal vein occlusion (first stage). Continuous data presented as median values were compared using Mann Whitney U test before and after PSM. The Two-tailed Fisher's Exact test was used for comparing categorical variables before and after PSM. A p-value of less than 0.05 was considered statistically significant. SPSS version 23.0 (IBM SPSS, Inc., Chicago, IL) software package was applied for data analysis.

[name], PhD,
Head of the HepatoPancreatoBiliary
Surgery Department,
Moscow Clinical Scientific Center
[contact]
www.mknc.ru

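### Stage-2 morbidity and blood loss are compared only among patients who reach stage 2, which the stage-1 procedure may itself influence, and no endpoint reports who gets there

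*Protocol*

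**What the plan says.** The Protocol (Material and Methods) defines the groups by procedure: "Group 1: patients with h-CCA and i-CCA underwent RALPPS" and "Group 2: patients with h-CCA and i-CCA underwent PVE". Under Inclusion Criteria, the patients are those "which are the candidates for radical treatment (intention to R0 resection"), "using major liver resection with volume of future liver remnant (FLR) less than 40" per cent. They therefore enter with resection as the goal, and stage 1 is there because the remnant is small.

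The main outcome is stated as "Primary endpoint: rate of FLR hypertrophy". Under Secondary endpoints, item 1 is stage-1 morbidity on the Clavien-Dindo scale, whose top grade is death. Item 2 is "Morbidity after stage 2" and item 3 is "Blood loss (during stage 2"). Item 4 is hospital stay, without saying which admissions count.

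The SAP (Statistical analysis) uses two matching models. The stage-1 model uses three jaundice and cholangitis factors. Of the other it says: "PSM model for stage 2 enrolled FLR volume after portal vein occlusion (first stage"). No other stage-2 factor is named.

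Neither document gives a denominator for the stage-2 endpoints, an endpoint for completing stage 2, or a rule for patients who start stage 1 and are never resected.

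**The concern.** Items 2 and 3 are conditional on an event that happens after treatment starts. FLR growth and stage-1 complications are likely determinants of that event, and both are outcomes on which the study compares the procedures. If the procedures differ on either, the patients who reach stage 2 may be selected differently in the two groups. A difference in stage-2 morbidity could then reflect who was resected and not what the procedure did. A strategy that leaves its frailer patients unresected would look safer at stage 2, and one that brings nearly everyone to resection would look more dangerous.

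This bears on a decision. The Protocol makes enlargement to 60 patients depend partly on the early results supporting the safety of RALPPS. If stage-2 morbidity informs that judgement, a rate among resected patients alone could mislead it. With completion reported nowhere, a reader could not tell.

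**Working it through.** The plan offers no figure to reproduce here: it states no completion rate, event rate, effect size or power. Every rate below is an assumption, chosen to show how the mechanism behaves.

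**1. Two risk strata, no true effect of procedure.** Assume 40% of patients are high-risk, with stage-2 morbidity of 30% (low-risk) and 70% (high-risk) under either procedure. Morbidity among completers = (0.6 × c_low × 0.30 + 0.4 × c_high × 0.70) / (0.6 × c_low + 0.4 × c_high), where c is the completion probability in each stratum.

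- RALPPS with c = 0.97 and 0.95: completion 0.582 + 0.380 = 0.962; morbidity (0.1746 + 0.2660) / 0.962 = 45.8%.
- PVE with c = 0.90 and 0.50: completion 0.540 + 0.200 = 0.740; morbidity (0.1620 + 0.1400) / 0.740 = 40.8%.
- Spurious difference: +5.0 points. Swapping the two patterns gives -5.0. Equal patterns (82% completion in each group) give 0.

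So the bias can go either way, and it vanishes when selection is the same in both groups.

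**2. Continuous frailty, no true effect.** Let Z be standard normal. P(complete | Z) = expit(a − bZ), with a set in each group to give the assumed completion c. P(event | Z) = expit(logit 0.30 + bZ), identical in both groups. Risk among completers = E[P(complete | Z) × P(event | Z)] / c. With 95% completion in one group, the spurious difference in percentage points is:

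| Log-odds b per SD | Other group 85% | 75% | 65% |
|---|---|---|---|
| 1.0 | 1.7 | 3.2 | 4.7 |
| 1.5 | 3.0 | 5.7 | 8.2 |
| 2.0 | 4.1 | 7.9 | 11.4 |

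The central cell is 33.7% v 28.0%.

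**3. Does the named stage-2 matching factor help?** Simulate 400,000 patients per group with no effect of procedure on morbidity. Baseline FLR has mean 30 and SD 5. Post-stage-1 FLR = baseline + 10 + extra RALPPS growth + 4U, where U is an unmeasured regenerative factor. Log-odds of morbidity = −0.4 − 0.8U. Patients reach stage 2 above an arbitrary FLR threshold, which is a modelling device and not a clinical rule.

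| Extra RALPPS growth (FLR points) | Difference among completers | After stratifying on post-stage-1 FLR |
|---|---|---|
| 0 | 0.1 | 0.1 |
| 5 | 4.5 | 8.3 |
| 10 | 7.1 | 16.6 |

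At equal post-stage-1 volume, a PVE patient got there with less help from the procedure and so tends to have a more favourable U. In this setting, conditioning on that volume enlarges the bias.

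**4. Which all-starter measure?** Take the central cell of step 2.

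- Events per starter: 33.7% × 0.95 = 32.0% v 28.0% × 0.75 = 21.0%. The gap grows from 5.7 to 11.0 points, because unresected patients are scored as event-free.
- Resected without a stage-2 event, per starter: 95.0 − 32.0 = 63.0% v 75.0 − 21.0 = 54.0%. This follows the assumed difference in completion, which is a real difference in what happened to patients.

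An invented small-number case shows the same. Suppose RALPPS resects 10/10 with 4 severe events and PVE resects 14/20 with 5. Among resected patients the event rates are 4/10 (40%) v 5/14 (36%). Events per starter are 4/10 (40%) v 5/20 (25%). Resected without a severe event, per starter, is 6/10 (60%) v 9/20 (45%). Only the last counts failure to reach resection against a strategy. None is distinguishable by Fisher's exact test (p = 1.00, 0.43 and 0.70).

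**The case against.** The strongest reply is that the plan is less blind than it looks. A reader might infer that patients lost between the stages are counted nowhere. The documents do not support that: death after stage 1 is Grade V stage-1 morbidity, and poor growth enters the primary endpoint if it is imaged. What stands is narrower. No endpoint counts failure to reach resection, and progression between the stages is counted nowhere.

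A second reply is that the magnitude is wholly assumed. That is correct. The range in step 2 starts from unequal completion and so leaves out the zero that arises under equal selection. A reader might also infer that the study will rank the strategies the wrong way round. The documents do not support that either. They give no completion rates, the primary endpoint does not depend on stage 2, and the small-number reversal arises from changing the question to resection without a severe event.

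Third, the SAP does not say that the stage-2 match is restricted to resected patients. That is a reasonable inference, not a stated fact. The objection to matching on a variable that treatment affects does not depend on it.

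Finally, these comparisons have little power anyway. For an assumed 40% v 20%, Fisher's test has 17.7% power at 10 v 20 and 29.8% at 30 v 30, even with every patient resected. That is true, but it argues for descriptive reporting and not for testing a selected subset.

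**Conclusion.** The concern holds as a point about two secondary endpoints. Stage-2 morbidity and stage-2 blood loss are conditional on reaching stage 2. That event plausibly depends on things the plan treats as outcomes of the stage-1 procedure, and the one stage-2 adjustment named cannot restore comparability and may make matters worse. Hospital stay shares the problem if it includes the stage-2 admission, which is not defined.

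Neither the size nor the direction of the bias can be derived from the documents. The figure of about 1.7 to 11.4 points rests on assumed completion of 95% v 65-85%, 30% morbidity at average frailty, and one frailty factor driving both non-completion and morbidity. The primary endpoint is not affected by this point. The change should be made, because without it the stage-2 safety comparison cannot be interpreted.

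**What to change.** Take all patients who started stage 1, in the stage-1 matched set, as the denominator for the between-group comparison, and compare:

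- (a) the proportion completing stage 2, with reasons for non-completion by group;
- (b) the proportion resected without severe morbidity or death from stage 1 through the stage-2 postoperative period, so that not reaching resection counts as a failure.

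Do not use severe morbidity per starter alone, for the reason in step 4. Report stage-2 morbidity and blood loss among resected patients as descriptive, labelled as conditional on reaching stage 2. Do not rely on matching on post-stage-1 FLR to make those patients comparable.

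The cost is wording in the Protocol and SAP and one extra table. The design is retrospective, so the information should come from patient records, although the documents do not confirm that reasons for non-completion were recorded. Pure stage-2 rates would no longer be the tested comparison. Measure (b) mixes non-resection with complications, so its components should be shown separately.

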Statistical analysis plan

Title of the study: Split-in-situ Resection With Radio-frequency Ablation Instead of Liver Partition on the First Stage (RALPPS) in Patients With Hilar and Intrahepatic Cholangiocarcinoma

Unic Protocol ID: MCNC 09/2017

Date: October 24, 2017

Statistical analysis

The propensity score matching (PSM) method was used to overcome heterogeneity of retrospectively collected data in compared groups. Nearestneighbor algorithm with 1:1 match ratio using a 0.2 caliper was applied. Matching for stage 1 included following factors: maximum total bilirubin level, duration of jaundice and acute cholangitis presence. PSM model for stage 2 enrolled FLR volume after portal vein occlusion (first stage). Continuous data presented as median values were compared using Mann Whitney U test before and after PSM. The Two-tailed Fisher's Exact test was used for comparing categorical variables before and after PSM. A p-value of less than 0.05 was considered statistically significant. SPSS version 23.0 (IBM SPSS, Inc., Chicago, IL) software package was applied for data analysis.

[name], PhD,
Head of the HepatoPancreatoBiliary
Surgery Department,
Moscow Clinical Scientific Center
[contact]
www.mknc.ru

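### The stage-1 primary comparison makes no adjustment for pre-procedure FLR, and dividing by it removes a baseline imbalance only if growth is proportional to the starting remnant

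*SAP*

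**What the plan says.** The protocol describes the design as "Study design: retrospective observational case-control study" and names "Primary endpoint: rate of FLR hypertrophy" in per cent. Under "The standard formula for calculation the rate of hypertrophy" it gives (post - pre)/pre x 100. Both procedures share one indication list with the same ceiling on the remnant ("h-CCA, type II-IV, T1-3N0-1M0, volume of FLR<40" per cent, and the same limit for i-CCA), and no lower limit is set.

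The SAP's Statistical analysis section uses 1:1 nearest-neighbour propensity matching with a caliper of 0.2. For stage 1: "Matching for stage 1 included following factors: maximum total bilirubin level, duration of jaundice and acute cholangitis presence". For stage 2: "PSM model for stage 2 enrolled FLR volume after portal vein occlusion (first stage". The test is then specified: "Continuous data presented as median values were compared using Mann Whitney U test before and after PSM". No regression or stratification is described, and the SAP does not say whether the comparison before or after matching is the primary one.

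The protocol sets a first step of 10 RALPPS and 20 PVE patients. Expansion to 30 per group is conditional: "If preliminary results reveal tendency to better results of RALPPS in terms of FLR hypertrophy and confirm safety of RALPPS".

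**The concern.** Pre-procedure FLR must be known for every patient, because it decides eligibility and enters the endpoint twice, as the value subtracted and as the divisor. Yet nothing in the stage-1 comparison balances it or conditions on it. The stage-2 FLR term cannot do so: it is measured after the first procedure and is itself a component of the primary outcome.

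A percentage change looks as if it deals with baseline, but in general it does not. A gain of 10 points is 10/25 = 40.0% from a remnant of 25 and 10/35 = 28.6% from a remnant of 35, and both patients would be eligible. If one procedure was used in patients with smaller remnants, and growth depends at least partly on something other than starting size, the endpoint differs between groups with no difference between procedures.

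Two uses of the result are exposed. One is the decision to expand, which rests on a tendency in hypertrophy plus safety and not on a p-value, so a directional bias enters it directly. The other is the later 30 v 30 comparison, where the same bias meets a larger sample.

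**Working it through.** The plan gives no effect size, SD or power, so there is no figure of its own to reproduce.

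**Inputs from the documents.** The endpoint formula, FLR below 40%, 10 v 20 then 30 v 30, the three stage-1 matching factors, caliper 0.2, Mann-Whitney, p < 0.05.

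**Assumptions not in the documents.** PVE baseline mean 30, SD 5, capped at 40; RALPPS mean lower by 2.5 or 5 points; no true effect; two-sided test. Growth is additive (10 points, SD 4), proportional (35%, SD 14%), or half of each.

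**Step 1: size of the spurious difference, before matching.** Putting nominal means of 25 and 30 into the formula:

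| Growth | RALPPS minus PVE at the means | Simulated median difference | Mann-Whitney rejection, 10 v 10 / 10 v 20 / 30 v 30 |
|---|---|---|---|
| Additive | 10/25 - 10/30 = 40.0 - 33.3 = 6.7 | 6.3 to 6.5 | 11 / 16 / 29% |
| Half-additive | (20.0 + 17.5) - (16.7 + 17.5) = 3.3 | 3.2 to 3.4 | 8 / 11 / 20% |
| Proportional | 35 - 35 = 0 | none | 4 to 5% |

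The cap reduces the nominal 5-point gap to 4.7. With a 2.5-point gap and additive growth the difference is 2.8 to 3.0 and rejection is 6 / 7 / 10%. If the gap runs the other way (35 v 30), the same arithmetic gives 28.6 - 33.3 = -4.8 (from unrounded values), against RALPPS.

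The rejection rates depend on the assumed scatter. With a gain of 11 points, SD 3, and means of 27 and 32, they are 21% (10 v 20) and 43% (30 v 30), while the false difference is still about 6 points.

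**Step 2: could chance alone produce the gap?** The SE of the baseline difference is 5 x sqrt(1/10 + 1/20) = 1.94 at the first step and 5 x sqrt(2/30) = 1.29 at 30 v 30. A gap of 2.5 points with RALPPS lower is 2.5/1.94 = 1.29 SE (about 10%) and 2.5/1.29 = 1.94 SE (about 3%). A gap of 5 points at 10 v 20 is 5/1.94 = 2.58 SE (about 0.5%), so it would need selection.

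**Step 3: after the planned matching.** Additive growth, 5-point gap. Further assumptions: 60% h-CCA, jaundice severity 0.6 SD higher in RALPPS, and caliper read as 0.2 SD of the logit. About 7.2 pairs result from 10 v 20 and 20.2 from 30 v 30.

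| Share of FLR gap carried by the biliary factors | Residual gap | Rejection, first step | Rejection, 30 v 30 |
|---|---|---|---|
| 0% | 4.7 | 10% | 22% |
| 25% | 4.4 | 7% | 19% |
| 50% | 4.0 | 6% | 16% |

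Matching on the three factors leaves most of the gap in place. Test inflation at the first step is small because so few pairs remain.

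**Step 4: does adjustment work?** Regressing log(post) on group and log(pre) lets the data set the slope: 1 under proportional growth, roughly 30/(30 + 10) = 0.75 under additive growth at the mean. Without measurement error its rejection rate under no effect is 4.3 to 6.3% unmatched, 4.2 to 5.6% in the matched sample, and 4.3 to 6.2% in the full sample with the three factors added.

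With measurement error the slope is attenuated. Take an assumed relative error of 8% and proportional growth. Log-baseline variance is (5/30)^2 = 0.0278 and error variance is 0.08^2 = 0.0064, so reliability is 0.0278/0.0342 = 0.81. The log gap is ln(25/30) = -0.182, and the leftover bias is -0.182 x 0.19 = -0.035, a ratio of about 0.97 against RALPPS. In simulation the regression then rejects about 8 to 9%, while Mann-Whitney stays near 4 to 5%. Under additive growth with the same error, at 30 v 30, regression is still the better of the two: 7.6% against 17.5%.

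**The case against.** The strongest reply is that the harm needs two things the documents do not show: a baseline gap, and growth not proportional to the starting remnant. Both procedures share one indication list and one FLR ceiling, no imbalance is reported, and under proportional growth the planned endpoint is unbiased. All of this stands. What it does not do is balance the groups below 40%, or justify the proportionality on which the planned analysis relies.

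A reader might infer that percentage hypertrophy never corrects for baseline, or that this plan is biased towards RALPPS. The documents support neither. The first fails under proportional growth; the second needs a direction of imbalance that is nowhere stated.

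A reader might also infer a high chance of a false decision to expand. In simulation at 10 v 20, with a 5-point gap and additive growth, the median difference favours RALPPS in 79% of unmatched samples, against 50% with no gap. But those samples are unmatched, the protocol does not define a tendency, so a median difference above zero is only one possible reading, and expansion also requires safety to be confirmed.

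Finally, the regression has its own weakness. With noisy volumetry and proportional growth it is the worse of the two analyses. That stands, and it is the reason not to replace the planned test.

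**Conclusion.** The gap in the plan is a matter of text: no part of the stage-1 comparison adjusts for pre-procedure FLR. Its consequence is conditional. With a baseline gap of about one assumed SD and no true effect, the spurious difference before matching is about 6.5 percentage points under additive growth, about 3.4 under half-additive growth and zero under proportional growth. Its sign follows the direction of the imbalance. After matching, the significance test at the first step is little affected; what matters is a spurious difference carried into the expansion judgement and into the 30 v 30 comparison. The baseline distribution, the gap, the growth model and the matching scenario are all assumptions.

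This supports a low-cost addition to the SAP. It does not show that the existing design is biased, nor that the Mann-Whitney comparison should be dropped.

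**What to change.** In the SAP:

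- Add a baseline-adjusted stage-1 analysis: regression of log(post-FLR) on group and log(pre-FLR) in the matched sample, and the same model in the full sample with the three biliary factors added.
- Report the adjusted ratio with its 95% CI beside the planned Mann-Whitney comparison of percentage hypertrophy.
- Tabulate pre-procedure FLR by group before and after matching.
- Base the tendency judgement for expansion on the adjusted ratio, read together with the unadjusted result. If the two disagree, say so and claim no tendency.
- The data are retrospective and the SAP is written in the past tense, so label the adjusted analysis post hoc if outcomes were already known.

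No new data are needed, since both volumes are required for the endpoint. The costs are one more model term in about 7 to 10 pairs at the first step, a log-linear assumption, and incomplete or reversed correction if FLR is measured with error, which is why both analyses are shown.

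Power is not lost in the scenario checked: 1.5-fold growth, that is 15 points against 10 from a baseline of 30, or 5/30 = about 17 percentage points, with additive growth and no imbalance. In the matched sample, regression has 39% against 33% for Mann-Whitney at the first step, and 81% against 76% at 30 v 30. The full-sample model reaches 63% and 93%, which is a reason to report it as well.

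### Tumour type (hilar or intrahepatic) is in neither propensity match, so an unequal mix could be read as an effect of RALPPS, chiefly on the secondary endpoints and at stage 2

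*SAP*

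**What the plan says.** The protocol describes the design as a "retrospective observational case-control study". Its purpose is to compare short-term results "in patients with hilar (h-CCA) and intrahepatic (i-CCA) cholangiocarcinoma". Both groups are mixed: in Group 1 "patients with h-CCA and i-CCA underwent RALPPS", and in Group 2 "patients with h-CCA and i-CCA underwent PVE". One indication list serves both procedures, but it has a separate line for each tumour type (the hilar line reads "h-CCA, type II-IV, T1-3N0-1M0, volume of FLR<40"%), and the stage contraindications also differ by type.

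The SAP (Statistical analysis) plans two propensity matches:
- Stage 1: "Matching for stage 1 included following factors: maximum total bilirubin level, duration of jaundice and acute cholangitis presence".
- Stage 2: "PSM model for stage 2 enrolled FLR volume after portal vein occlusion (first stage").

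The "algorithm with 1:1 match ratio using a 0.2 caliper was applied". Continuous data are compared by Mann-Whitney U and categorical data by two-tailed Fisher's exact test, before and after matching. The SAP mentions no stratification, covariate adjustment or display by tumour type. The primary endpoint is the rate of FLR hypertrophy. The secondary endpoints are morbidity after each stage, blood loss during stage 2, and hospital stay. The first look has 10 RALPPS and 20 PVE patients, with a possible extension to 30 per group.

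**The concern.** Matching is the plan's only protection against baseline differences between groups that were not randomised. Tumour type defines the study population and is known for every patient, and the protocol itself separates the two types in its eligibility rules. Yet neither match uses it.

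The stage 1 factors all reflect biliary obstruction, so they may stand in for tumour type to some degree. An h-CCA patient without jaundice can still be paired with an i-CCA patient without jaundice, and likewise for jaundiced patients. The stage 2 model contains only FLR volume, which nothing in the documents makes a marker of tumour type. Morbidity after stage 2 and blood loss during stage 2 depend on that comparison.

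If one group holds more patients of the type with worse outcomes, the unadjusted tests will attribute that to the procedure.

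**Working it through.** **What can be reproduced.** The documents give no tumour mix, no outcome by type and no power calculation, so there is no planned figure to reproduce. All rates below are assumptions, used only to show scale.

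**1. How far the stage 1 factors balance type.** Simplify the match to exact agreement on jaundice (yes/no). Let pR and pP be the h-CCA shares in RALPPS and PVE, and jh and ji the jaundice rates in h-CCA and i-CCA.
- Jaundiced share of RALPPS: J = pR·jh + (1−pR)·ji
- h-CCA share among jaundiced PVE patients: a = pP·jh / [pP·jh + (1−pP)·ji]
- h-CCA share among non-jaundiced PVE patients: b = pP(1−jh) / [pP(1−jh) + (1−pP)(1−ji)]
- Residual gap = pR − [J·a + (1−J)·b]

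Low end (pR 0.80, pP 0.50, jh 0.95, ji 0.10): J = 0.78, a = 0.475/0.525 = 0.905, b = 0.025/0.475 = 0.053. The matched PVE share is 0.717, so the residual is 0.083.

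High end (pR 0.50, pP 0.80, jh 0.70, ji 0.30): J = 0.50, a = 0.56/0.62 = 0.903, b = 0.24/0.38 = 0.632. The matched PVE share is 0.767, so the residual is 0.267 in size.

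| Assumed jaundice rate, h-CCA / i-CCA | Residual of a 30-point gap (80% v 50%, either direction) |
|---|---|
| 95% / 10% | 8 to 10 points |
| 90% / 10% | 11 to 14 points |
| 85% / 20% | 17 to 20 points |
| 70% / 30% | 25 to 27 points |

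A simulation of 1:1 nearest-neighbour matching with a 0.2 caliper at 85% / 20% left 20 to 22 points, so the simplification does not exaggerate the problem.

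**2. What a residual gap does to a rate.** False difference = residual gap × the outcome difference by type that remains after matching. Assume complication rates of 45% in h-CCA and 20% in i-CCA, a difference of 25 points.
- Stage 1, if all 25 points remain among matched patients: 0.083 × 25 = 2.1 to 0.267 × 25 = 6.7 points. At 85% / 20%: 0.17 × 25 = 4.3 to 0.20 × 25 = 5.0.
- Stage 1, if matching on obstruction removes half of the outcome difference: 0.083 × 12.5 = 1.0 to 0.267 × 12.5 = 3.3 points. If it removes all of it: 0.
- Stage 2, if FLR volume balances nothing and the full difference remains: 0.30 × 25 = 7.5 points.

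**3. What it does to the tests.** For a categorical endpoint with h-CCA shares of 70% v 50%, the rates are 20 + 0.70 × 25 = 37.5% and 20 + 0.50 × 25 = 32.5%. Exact enumeration of the two-tailed Fisher test gives significance in about 1.5% of trials at 10 v 10 and 3.8% at 30 v 30.

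For a continuous endpoint with no true RALPPS effect, bias in SD units = D × gap in mix, where D is the outcome difference by type. False-positive rates come from 8,000 simulated Mann-Whitney tests per setting:

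| Mix | D (SD) | Bias (SD) | 10 v 10 | 10 v 20 | 30 v 30 |
|---|---|---|---|---|---|
| any | 0 | 0 | 4% | 4–5% | 5% |
| 60% v 40% | 0.5 | 0.1 | 5% | 5% | 6% |
| 70% v 30% | 0.5 | 0.2 | 6% | 6% | 11% |
| 60% v 40% | 1 | 0.2 | 5% | 7% | 11% |
| 70% v 30% | 1 | 0.4 | 11% | 14% | 28% |

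A systematic gap therefore matters more after the extension than at the first look.

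**The case against.** **Bias is conditional.** It needs both a different mix and a different outcome by type. A reader might infer from the omission that the groups do differ in disease. The documents do not support that: the shared indication list gives no reason for the mix to differ, and none for it to be equal. This objection stands, and the point is about exposure to bias rather than demonstrated bias.

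**The primary endpoint.** A reader might extend the concern to FLR hypertrophy. The documents offer nothing that links tumour type to hypertrophy, and if D = 0 there is no bias whatever the mix. This stands, so the concern is mainly for the secondary endpoints. That the types differ in complication risk is itself a clinical assumption.

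**Stage 1 already blocks part of the path.** If the types differ in risk because of biliary obstruction, matching on bilirubin, jaundice duration and cholangitis removes some of that difference. Multiplying the residual gap by the full 25 points then overstates the effect, so 5 points at 85% / 20% is nearer an upper bound than an estimate. This stands for stage 1. It does not help a stage 2 model that contains only FLR volume.

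**The purpose can still be answered.** A reader might say that a pooled study cannot meet its aim. The declared aim covers the combined population, so pooling is a legitimate choice; what is missing is balance on type within it.

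**A balance check is not excluded.** Fisher's test is planned for categorical variables before and after matching, which could include tumour type, although it is not named. This helps little at these sizes: with h-CCA in 8 of 10 v 5 of 10, a 30-point gap, the two-tailed p is 2 × (45·252 + 10·210 + 1·120)/77,520 = 0.35.

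**Conclusion.** The gap is real and should be closed as a cheap improvement; it is not an error that invalidates the study. The documents establish that the types are pooled without randomisation, that tumour type is in neither match, and that the named endpoint tests are unadjusted. They do not establish that the mix differs, that outcomes differ by type, or that the primary endpoint is affected.

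Under the assumed rates, about 8 to 27 points of a 30-point gap survive the stage 1 match. The resulting false difference in a complication rate runs from 0 to about 7 points, depending on how much of the outcome difference by type remains. Stage 2 is the weakest place, with up to 7.5 points on the same assumptions. False-positive rates move little at 10 pairs unless both the mix gap and the type effect are large; at 30 v 30 they reach 11% to 28% in the less favourable settings.

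**What to change.** In the SAP:
- Add tumour type (h-CCA or i-CCA) to both the stage 1 and the stage 2 propensity models.
- Report the balance of tumour type before and after each match as counts and a standardised difference, not only a p-value.
- Stratify the endpoint comparisons by type: van Elteren test for continuous endpoints, stratified exact test for categorical ones. Confirm that the named software runs both, or name another package.
- Show each endpoint by tumour type, descriptively.
- Use exact matching on type only if enough pairs remain, for example at 30 v 30. It should not be the default at the first look, where 1:1 matching gives at most 10 pairs.

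No new data are needed, because type is an eligibility item. The cost is a few sentences in the SAP, possibly fewer matched pairs, and sparse strata at 10 v 20, where results by type will be too thin for inference.
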